**Table 1 - SVR12 rates in clinical trials:**

Population and treatment duration	Genotype	SVR12 ABBVIE REGIMEN + RBV	SVR12 ABBVIE REGIMEN alone
Non-cirrhotic, treatment-naïve (12 weeks)	1a	95-97% (SAPPHIRE-I, PEARL-IV)	90% (PEARL-IV)
	1b	98-99.5% (SAPPHIRE-I, PEARL-III)	99% (PEARL-III)
Non-cirrhotic, treatment-experienced (12 weeks)	1a	96% (SAPPHIRE-II)	n.a.
	1b	97% (SAPPHIRE-II, PEARL-II)	100% (PEARL-II)

Confidential Information

No use or disclose outside AbbVie is permitted without prior written authorization from AbbVie  
The Netherlands v 1.4 (26 March 2018). Protocol based on AbbVie shell protocol version 3.0 (22 April 2015) Page 17 of 65

These results suggest that the ABBVIE REGIMEN with RBV is the optimal regimen for genotype 1a infected patients, while patients with genotype 1b do not require RBV.

The TURQUOISE-II [60] study explored the efficacy of the ABBVIE REGIMEN in the traditionally most difficult-to-treat cirrhotic patients. This large study enrolled exclusively genotype 1 infected patients with cirrhosis, including treatment-naïve and treatment-experienced individuals. All patients received the ABBVIE REGIMEN with RBV and were randomized to 12 or 24 weeks of therapy. Overall 92% and 96% of patients achieved SVR following treatment for 12 or 24 weeks, respectively. Analysis of subgroups demonstrated that the small difference in SVR between treatment arms was due largely to the subgroup of genotype 1a treatment-experienced prior null responders treated for 12 weeks who achieved an SVR of 80%. This subgroup of patients achieved an SVR of 93% when treated for 24 weeks. Among genotype 1a infected patients, partial responders and relapsers had higher SVR rates than null responders in the 12 week treatment group, while similar SVR rates were seen among the null responders, partial responders and relapsers treated for 24 weeks, suggesting that the longer duration of 24 weeks is required only for cirrhotic genotype 1a null responders. SVR rates were very high across all subgroups in genotype 1b treatment-experienced patients treated for 12 and 24 weeks.

The ABBVIE REGIMEN has been studied with and without RBV in over 2,300 patients in Phase III trials across a variety of patient populations including those with compensated cirrhosis. Based on Phase III data, the ABBVIE REGIMEN, with or without RBV, was well tolerated with a low discontinuation rate. Adverse events (AEs) were typically mild, and many of the AEs and laboratory abnormalities reported were attributable to the presence of RBV. However, these AEs were much milder than observed when RBV was given in combination with interferon. Transient, asymptomatic serum alanine aminotransferase (ALT) elevations were observed at a low rate, were not associated with hepatic dysfunction and generally resolved with ongoing treatment. A disproportionate number of the cases were in women on concurrent ethinyl estradiol-containing therapy (i.e., contraceptives or hormone replacement) and discontinuation of the hormonal therapy with continuation or brief interruption of the ABBVIE REGIMEN led to resolution in serum ALT elevation. Transient elevations in serum bilirubin (predominantly indirect) were observed in subjects receiving the ABBVIE REGIMEN with RBV, related to the inhibition of the bilirubin transporters, organic anion-transporting polypeptides (OATPs) 1B1/1B3, by paritaprevir and RBV-induced hemolysis. Bilirubin elevations occurred after initiation of treatment, peaked by study Week 1, and generally resolved with ongoing therapy.

---

**Confidential Information**

---

Bilirubin elevations were not associated with aminotransferase elevations. The frequency of indirect bilirubin elevations was lower among subjects who did not receive RBV.

Response of CHC genotype 4 was assessed in the phase II study PEARL-I in which 86 treatment-naive patients were randomized to the 2 DAA combinations of paritaprevir /r – ombitasvir with vs. without RBV for 12 weeks. The SVR was 100% with RBV vs. 91% without RBV [61]. No serious SAEs or AEs leading to discontinuation were reported.

These results from pivotal studies are encouraging and the new interferon-free regimens might provide physicians with the armamentarium to cure the vast majority of patients infected with CHC. However, the medical community is expecting data which show how these results translate into routine clinical practice particularly after the experience with the first protease inhibitors which were available to physicians and where the outcome in everyday life and especially the tolerability was far less favorable in certain difficult-to-treat patient subgroups than expected from the development trials [62] [63].

## 7.2 Rationale

The ABBVIE REGIMEN ± RBV for the treatment of CHC has been shown to be safe and effective in randomized controlled clinical trials with strict inclusion and exclusion criteria under well controlled conditions.

The ABBVIE REGIMEN is expected to be first available in the Netherlands for the treatment of CHC in 2015.

The rationale for this observational study is to determine how the efficacy and safety of the ABBVIE REGIMEN as demonstrated in pivotal trials translates into real world everyday clinical settings, evaluating its effectiveness. Whereas efficacy can be defined as a measure of the capacity of a treatment to produce the desired effect in a controlled environment, such as in a randomized controlled trial, effectiveness is 'the extent to which a drug achieves its intended effect in the usual clinical setting' [64]. Effectiveness trials typically have limited exclusion criteria and will involve the broader patient populations in routine clinical practice, treated per local label, which might include patients with heterogeneous compliance patterns and patients with significant comorbid conditions and could be used to model and disseminate best practices. Effectiveness research allows for external patient-, provider-, and system-level factors and can therefore be relevant for health-care decisions by both providers in practice and policy-makers [65].

---

This observational study is the first effectiveness research examining the ABBVIE REGIMEN ± RBV, used according to local label, under real world conditions in the Netherlands in clinical practice patient population.

During the last decade when dual therapy with pegIFN plus RBV was standard of care for the treatment of CHC, management of patients and clinical outcome were improved following the discovery of predictive factors of virological response, often in observational studies with large data bases [66]. Thus treatment could be targeted to patients most likely to respond and futile treatment stopped in patients with a low likelihood of virological cure. HCV genotype and subtype, baseline viral load, fibrosis stage, age, treatment exposure and on-treatment virological response proved to be useful predictors for the eradication of HCV in everyday clinical practice [27]. The discovery of a genetic disposition of the Interleukin 28B (IL28B) single nucleotide polymorphism (SNP) contributed further to our understanding of virological responses to PegIFN and RBV regimen [67]. For new interferon-free treatment regimens knowledge of predictive factors of virological response is extremely sparse and several of the now well established predictors of response were not initially identified through analyses of the development trials. This observational study may play an important part in bridging the data gaps and could help identify predictive factors of virological response in everyday clinical settings which were not detected in interventional trials and which could be used to further optimize treatment with the interferon-free ABBVIE REGIMEN in the future.

The label of the ABBVIE REGIMEN will vary according to HCV genotype/subtype and stage of liver disease. It is therefore relevant to understand the pattern of use and outcome in daily clinical practice. In addition, this study will provide data on the impact of adherence on treatment outcomes in everyday settings, which may help treating physicians to improve the management of patients under their care.

The aim of this observational study is to provide evidence of the effectiveness, tolerability, adherence, healthcare resource utilization, quality of life and work productivity of the ABBVIE REGIMEN ± RBV in a real world setting across clinical practice patient populations.

## **8.0 Research Question and Objectives**

### **8.1 Research Question**

What is the effectiveness, tolerability, adherence, healthcare resource utilization, quality of life and work productivity of the interferon-free ABBVIE REGIMEN ± RBV in patients with CHC in a real life setting across clinical practice patient populations?

### **8.2 Objectives**

#### **8.2.1 Primary Objective**

1. To describe in routine clinical practice the effectiveness of the interferon-free ABBVIE REGIMEN ± RBV in patients with CHC as evidenced by SVR12

#### **8.2.2 Secondary Objectives**

1. To describe the pattern of real world use of the ABBVIE REGIMEN ± RBV with respect to different patient and treatment characteristics
2. To evaluate the influence of adherence on treatment outcome in routine clinical practice
3. To describe the tolerability of the ABBVIE REGIMEN ± RBV
4. To document the effect of the ABBVIE REGIMEN ± RBV on PROs and work productivity in the Dutch population
5. To determine the impact of the ABBVIE REGIMEN ± RBV on healthcare resource utilization

## **9.0 Research Methods**

### **9.1 Study Design**

This is a prospective, multi-center observational study in patients receiving the interferon-free ABBVIE REGIMEN with or without RBV. The prescription of a treatment regimen is at the discretion of the physician in accordance with local clinical practice and label, is made independently from this observational study and precedes the decision to offer the patient the opportunity to participate in this study.

Adult patients chronically infected with HCV, receiving the interferon-free ABBVIE REGIMEN will be offered the opportunity to participate in this study during a routine clinical visit at the participating sites.

---

Confidential Information

No use or disclose outside AbbVie is permitted without prior written authorization from AbbVie

The Netherlands v 1.4 (26 March 2018). Protocol based on AbbVie shell protocol version 3.0 (22 April 2015) Page 21 of 65

[figure not shown]
After written informed consent has been obtained, patient data including demographic data, HCV disease characteristics, co-morbidities, co-medication, treatment details, and laboratory assessments as recorded in the patient's medical records (source documentation) will be documented in the electronic case report form (eCRF). Patients will be observed for the duration of the ABBVIE REGIMEN therapy and for up to 24 weeks after treatment completion. No patient identifiable information will be captured, a unique patient number will be automatically allocated by the web based eCRF system once the investigator or designee creates a new patient file.

This study is focusing on collecting real-world data. Follow-up visits, treatment, procedures and diagnostic methods will follow physicians' routine clinical practice. The observational study period entails the following data collection schemes, data documented will be those closest to the time windows as indicated in Figure 1:

- 12-week treatment regimen: four visits plus two interim data collection windows
- 24-week treatment regimen: four visits plus three interim data collection windows

This schedule is based on the anticipated regular follow-up for patients undergoing treatment for CHC.

Figure 1 - Study Flowchart

Confidential Information

## **9.2 Setting**

For overall research design and observational documentation schedule refer to Sections 9.1 and 9.4.1 as well as to Figure 1.

### **9.2.1 Target Population**

Patients are eligible for observation in this cohort if the following applies:

- Treatment-naïve or -experienced adult male or female patients (age  $\geq 18$  yrs) with confirmed CHC, genotype 1 or 4, receiving combination therapy with the interferon-free ABBVIE REGIMEN  $\pm$  RBV according to standard of care and in line with the current local label
- If RBV is co-administered with the ABBVIE REGIMEN, it has been prescribed in line with the current local label (with special attention to contraception requirements and contraindication during pregnancy)
- Patients must be able to speak and understand the Dutch language at such a level that they can understand and sign the informed consent and be able to understand and complete the questionnaires without any external help
- Patients must voluntarily sign and date informed consent prior to inclusion into the study

Patients are not eligible for observation in this cohort if the following applies:

- Patients participating or intending to participate in a concurrent interventional therapeutic trial
- Patients who are unable to complete the questionnaires due to cognitive impairment or lack of any kind of cognitive competence, as to be judged by the healthcare professional who is treating the patient
- Patients who are unable to complete the questionnaires due to language incompetence
- Patients who are unable to voluntarily sign and date the informed consent
- Patients included for treatment who do not meet the treatment criteria as described in the current label

---

Confidential Information

No use or disclose outside AbbVie is permitted without prior written authorization from AbbVie

The Netherlands v 1.4 (26 March 2018). Protocol based on AbbVie shell protocol version 3.0 (22 April 2015) Page 23 of 65

## 9.2.2 Study Duration

This is a prospective, observational study. The inclusion period will be approximately 12 months and the observational period of the study will be from baseline visit until 24 weeks post-treatment.

The observational period for patients receiving 12 weeks of ABBVIE REGIMEN will be max. 36 weeks (12 weeks treatment and 24 weeks post-treatment observation) and for patients receiving 24 weeks of ABBVIE REGIMEN the observational period will be max. 48 weeks (24 weeks treatment and 24 weeks post-treatment observation).

### 9.2.3 Termination Criteria

For patients who terminate the ABBVIE REGIMEN prematurely for whatever reason the EoT eCRF page should be filled in and the reason for treatment discontinuation should be documented. If the reason for ABBVIE REGIMEN discontinuation is due to an SAE, the event must be reported to AbbVie within 24 hours of physician awareness (see Section 11.1.5).

If, in such patients, there is evidence of virological response during therapy or at EoT, the SVR12 and SVR24 pages should be completed if respective data is available.

### 9.2.4 Investigator Selection Criteria

University centers and outpatient clinics qualified by training and experience in the management of patients with CHC will be selected to participate in this study. The sites participating in the study should be representative of the medical practice, have the ability to conduct the study and their availability of the target patient population. The type of the participating treating institute will be documented in the eCRF.

## **9.3 Variables**

### **9.3.1 Primary Variable**

- The percentage of patients achieving SVR12 (HCV RNA <50 IU/mL 12 weeks [i.e. ≥70 days] after the last actual dose of the ABBVIE REGIMEN)

### **9.3.2 Secondary Variables**

- Type of treatment regimen ( $\pm$  Dasabuvir,  $\pm$  RBV, intended and actual combination, dose and duration)
- Adherence
  - Percentage of the DAA dose taken in relation to the target dose of DAA (cumulative dose taken divided by target dose in percent)
  - Percentage of the RBV dose taken in relation to the target dose of RBV (cumulative dose taken divided by target dose in percent)
  - Percentage of missed RBV treatment days in relation to the target number of RBV treatment days
- Serious and non-serious adverse events and pregnancy occurrences
- Questionnaires on PROs: e.g. EuroQol 5 dimension 5 level (EQ-5D-5L) questionnaire and work productivity and activity impairment (WPAI) questionnaire prior to treatment initiation, at EoT as well as 12 and 24 weeks after EoT
- Questionnaire on healthcare resource utilization

## **9.4 Data Sources**

Source documents are defined as original documents. The investigator will document patient data in his/her own patient files which will serve as source data for the study. Data are collected from the source documents for each patient in the study, consisting of medical records containing demographic data, medical, treatment and diagnostic documentation and laboratory assessments.

The investigator(s)/institution(s) will permit study-related monitoring, audits, independent ethics committee/- review board (IEC/IRB) review, and regulatory inspection(s), providing direct access to source data documents.

## **9.4.1 Data to be Documented**

This observational study covers three documentation periods, see Figure 1. An overview on data to be collected throughout the study is summarized in Table 2.

After the patient has signed informed consent, the following data will be documented in the eCRF, if available from the patient charts based on assessments done in physicians' routine clinical practice.

### **9.4.1.1 Inclusion Documentation**

Inclusion:

Patients will be included only after the physician and the patient have decided to treat chronic HCV with paritaprevir/r and ombitasvir +/- dasabuvir +/- ribavirine. To guarantee independence of prescription choice of the HCP, a nurse practitioner will check if a newly prescribed patient might be eligible for the study and if so, may inform the patient about participation in the observational study.

Patients can be enrolled in the PMOS during the first 4 weeks of treatment, enabling the nurse practitioner to search eligible newly prescribed patients also from medical records.

After the patient has been found eligible and after the informed consent has been signed, the following will be documented if available:

- Demographic information
  - Interleukin 28B (IL28B) genotypes
- CHC disease characteristics
  - Year of diagnosis and mode of infection
  - Stage of liver fibrosis/cirrhosis (Annex 4)
- CHC treatment history
  - Naïve or experienced
  - If experienced, most recent prior therapy and outcome
- Relevant medical history, co-morbidities and co-infections
- Concomitant medication, see 9.4.1.5
- ABBVIE REGIMEN ± RBV

- Laboratory data

Key clinical chemistry	Remarks
▪ ALT (alanine-aminotransferase)	including upper limit of normal (ULN),
▪ AST (aspartate-aminotransferase)	including ULN, AST to platelet ratio index (APRI) and Fibrosis-4 Score/Index (FIB-4)* will be calculated
▪ γ-GT (gamma-glutamyltransferase)	
▪ Total bilirubin	
▪ Albumin	
▪ Creatinine	creatinine clearance # will be calculated
▪ AFP	
Key hematology	
▪ Hb (Hemoglobin)	
▪ Platelets	
▪ Prothrombin time	or international normalized ratio (INR)
Virology	
▪ HCV genotype and subtype	
▪ HCV RNA	quantitative/ qualitative HCV RNA by polymerase chain reaction (PCR) test, see 9.4.1.4
HIV-infected patients only	
▪ CD 4 count (cluster of differentiation 4)	most recent assessment
▪ HIV RNA	in copies/mL

\*derived from patient's age, ALT, AST and platelets

#by Cockcroft-Gault-Formula based on creatinine, gender, age and weight

- Patient questionnaires, see Table 2 and 9.4.1.6
- Treatment related health care resource utilization

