##### Confidential Information

No use or disclose outside AbbVie is permitted without prior written authorization from AbbVie

The Netherlands v 1.4 (26 March 2018). Protocol based on AbbVie shell protocol version 3.0 (22 April 2015) Page 27 of 65

The following will be documented if available:

- Laboratory data

Key clinical chemistry

- ALT
- AST
- $\gamma$ -GT
- Total bilirubin
- Creatinine

Remarks

- including ULN
- including ULN,  
APRI and FIB-4 will be calculated
- creatinine clearance will be calculated

Key hematology

- Hb
- Platelets

Virology

- HCV RNA

quantitative/ qualitative HCV RNA PCR test, see 9.4.1.4

HIV-infected patients only

- CD 4 count
- HIV RNA

most recent assessment  
in copies/mL

- Concomitant medication, see 9.4.1.5
- Adherence to ABBVIE REGIMEN  $\pm$  RBV as established by interviewing the patient during regular visits
- Tolerability (sAEs and AEs, see 11.1.5) and pregnancies (see 11.1.6)
- Patient questionnaires see 9.4.1.6
- Treatment related health care resource utilization

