**Confidential Information**

**No use or disclose outside AbbVie is permitted without prior written authorization from AbbVie**

The Netherlands v 1.4 (26 March 2018). Protocol based on AbbVie shell protocol version 3.0 (22 April 2015) Page 28 of 65

The following will be documented:

- Laboratory data

Key clinical chemistry

- ALT
- AST
- $\gamma$ -GT
- Total bilirubin
- Albumin
- Creatinine

Remarks

including ULN  
including ULN,  
APRI and FIB-4, will be calculated

creatinine clearance will be calculated

Key hematology

- Hb
- Platelets
- Prothrombin time

or INR

Virology

- HCV RNA

quantitative/ qualitative HCV RNA PCR test, see 9.4.1.4

HIV-infected patients only

- CD 4 count
- HIV RNA

most recent assessment  
in copies/mL

- Tolerability (sAEs, see 11.1.4) and pregnancies (see 11.1.6)
- Patient questionnaires see 9.4.1.6

---

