### **11.1.4                   Serious Adverse Event Collection Period**

SAEs will be reported to AbbVie from the time the physician obtains the informed consent until 30 days or 5 half-lives following the intake of the last dose of physician-prescribed treatment.

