### **11.1.5                   Serious and non-serious Adverse Event Reporting**

In the event of an **SAE**, the physician will:

- For events from patients using the ABBVIE REGIMEN ± RBV (or any other AbbVie authorized product) report to AbbVie within 24 hours of the physician

---

Confidential Information

No use or disclose outside AbbVie is permitted without prior written authorization from AbbVie  
The Netherlands v 1.4 (26 March 2018). Protocol based on AbbVie shell protocol version 3.0 (22 April 2015) Page 45 of 65

---

becoming aware of the event by using the eCRF system or notifying the AbbVie contact person identified in Section 11.0.

- For events from patients using a non-AbbVie product - notify the Marketing Authorization Holder (MAH) of the product within 24 hours of the physician becoming aware of the event.

In the event of a ***non-serious AE***, the physician will:

- For events from patients using the ABBVIE REGIMEN ± RBV report to AbbVie by using the eCRF system.

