**Confidential Information**

*Please document for each hospitalization period in the 4 weeks prior to starting the ABBVIE REGIMEN the number of hospitalization days, the technical interventions performed and the symptoms treated:*

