**Technical Intervention(s) performed****Symptom(s) treated****Adverse Events:**

*If any of the treated symptoms is an Adverse Event, please report this Adverse Event additionally in the unscheduled records section.*

Hospitalization period(s) - Resource Utilization (since last visit)Hospitalization period(s) since last visit:

*Please document for each hospitalization period since last visit the number of hospitalization days, the technical interventions performed and the symptoms treated.*

*Duration*

Technical Intervention(s) performed

Symptom(s) treated

Adverse Events:

If any of the treated symptoms is an Adverse Event, please report this Adverse Event additionally in the unscheduled records section.

Serious Adverse Events:

Each unplanned hospitalization during therapy or within 30 days thereafter is considered to be an SAE and must be reported additionally on an Adverse Event page in the unscheduled records section.

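### Patients may enrol up to 4 weeks into treatment, but the SAE collection start conflicts with the treatment-emergent window and no visible rule defines the questionnaire baseline for them

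*Protocol*

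**What the plan says.** **Enrolment.** Protocol 9.4.1.1: "Patients can be enrolled in the PMOS during the first 4 weeks of treatment". The stated reason is that eligible patients can then also be found from medical records. The same section lists the patient questionnaires among the items documented after consent.

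**SAE collection.** Protocol 11.1.4, the only section headed as the SAE collection period: "SAEs will be reported to AbbVie from the time the physician obtains the informed consent until 30 days or 5 half-lives" after the last dose.

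**SAE analysis.** Protocol 9.7.6 and SAP 4.2.8.3 define an event as treatment-emergent if it starts or worsens after the first dose and up to 30 days after dosing. The serious-event tables use the same definition. The safety population (SAP 4.2.1) is every enrolled patient with at least one dose and a known prescribed regimen.

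**Text pointing to fuller capture.** Protocol 9.4.1: "After the patient has signed informed consent, the following data will be documented in the eCRF, if available from the patient charts". Protocol 9.4.1.2 includes SAEs and AEs among the on-treatment items and refers to 11.1.5, which states no consent limit: "For events from patients using the ABBVIE REGIMEN ± RBV (or any other AbbVie authorized product) report to AbbVie within 24 hours". Protocol 9.7.6 asks for all SAEs in included patients. Annex 1 adds: "Each unplanned hospitalization during therapy or within 30 days thereafter is considered to be an SAE and must be reported". Only the post-treatment item in Protocol 9.4.1.3 refers to 11.1.4.

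**Questionnaires.** The Protocol Abstract, Protocol 9.3.2 and SAP 4.1.2 place the first EQ-5D-5L and WPAI before treatment starts. SAP 4.2.7.2.2 summarises the EQ-5D-5L at baseline, after baseline and as change from baseline. It tabulates WPAI at baseline and later, restricted to employment status and absenteeism. SAP 4.2.2 limits baseline to study day 1 or earlier in Table 2 (HCV RNA) and Table 3 (safety laboratory data) only.

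**The concern.** A patient who consents after the first dose has a stretch of treatment that counts in the serious-event analysis but lies outside the collection period of Protocol 11.1.4. Two sites could follow different sections, both in good faith, and one would report an SAE that the other leaves out. Where it is left out, the patient stays in the denominator and the event is missing from the numerator, so the serious-event percentages (the tolerability objective) would be too low.

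The same patient cannot have completed a study questionnaire before treatment. The EQ-5D-5L asks about health on the day of completion (Annex 2), so the pre-treatment state cannot be recovered later. If the inclusion questionnaire is taken as baseline, the change score compares one post-dose state with another, and the bias can go either way. WPAI covers the preceding seven days, so a form completed from study day 8 onwards describes only time on treatment, yet could be tabulated as baseline absenteeism. Baseline questionnaire results were already tabulated in the March 2017 interim analysis (SAP 4.2.9), so the question applies to that table too.

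**Working it through.** The plan gives no figure to reproduce. Protocol 9.5 says the study size has no statistical basis and that 50-55 patients are expected. The check compares the time windows and then bounds the size.

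**1. Windows for a patient consented d days after first dose**

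| Item | Starts at | Source |
|---|---|---|
| SAE collection | consent (day d) | Protocol 11.1.4 |
| Serious treatment-emergent events | first dose (day 0) | Protocol 9.7.6; SAP 4.2.8.3 |
| Observation | covers the full 12 or 24 treatment weeks | Protocol 9.1, 9.2.2 |
| HCV RNA and laboratory baseline | study day 1 or earlier | SAP 4.2.2, Tables 2 and 3 |
| EQ-5D-5L and WPAI baseline | described as pre-treatment; no handling rule | Protocol 9.3.2; SAP 4.1.2, 4.2.7.2.2 |

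**2. Share of the treatment-emergent window before consent**

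Share = d / (T + 30), with T = 84 or 168 days and d at most 28.

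- 12 weeks: 28 / (84 + 30) = 28/114 = 24.6%. At d = 14: 14/114 = 12.3%.
- 24 weeks: 28 / (168 + 30) = 28/198 = 14.1%. At d = 14: 14/198 = 7.1%.

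These are bounds per patient, not estimates of bias.

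**3. Expected patients whose SAE is left out, if every site followed 11.1.4**

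Expected number = N × SAE risk × share consented late × d / (T + 30). N = 55 suits the safety population, which is all enrolled dosed patients. The other inputs are assumptions: risk 2-10%, share consented late 10-100%, lag 14-28 days, at most one SAE per patient, risk spread evenly over the window.

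| Case | 12 weeks | 24 weeks |
|---|---|---|
| Low | 55 × 0.02 × 0.10 × 14/114 = 0.014 | 55 × 0.02 × 0.10 × 14/198 = 0.008 |
| Middle | 55 × 0.05 × 0.50 × 14/114 = 0.17 | 55 × 0.05 × 0.50 × 14/198 = 0.10 |
| High | 55 × 0.10 × 1.00 × 28/114 = 1.35 | 55 × 0.10 × 1.00 × 28/198 = 0.78 |

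Divided by 55, the range is 0.02 to 2.5 percentage points (12 weeks) or 0.01 to 1.4 (24 weeks). For comparison, an illustrative 3/55 has a Wilson 95% interval of 1.9% to 14.9%. If SAEs cluster early in treatment, the even-spread assumption understates the loss.

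**4. EQ-5D-5L change**

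Bias in the mean change = share of analysed patients with an on-treatment baseline × mean difference between that score and the unobserved pre-treatment score. Both inputs are assumed:

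- 0.10 × 0.02 = 0.002 index points
- 0.25 × 0.05 = 0.0125
- 0.50 × 0.10 = 0.05

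The sign is unknown.

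**The case against.** The best reply on SAEs is that the protocol as a whole intends full on-treatment capture. Protocol 9.1 observes patients throughout therapy, and 9.2.2 counts all treatment weeks with no deduction for late consent. The consent rule in Protocol Table 2 governs when data may be entered, not when an event must have started. Sections 9.4.1, 9.4.1.2 and 9.7.6 and Annex 1 then ask for on-treatment events with no consent limit. On this view 11.1.4 says only when the duty to report begins. This stands as a possible reading, and it is why a loss of SAEs cannot be called certain. It does not remove the conflict: 11.1.4 is headed as a collection period and names consent as its start, and Annex 1 covers only unplanned hospitalisations.

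On the questionnaires, the reply is that a first form described three times as pre-treatment already excludes a late one, so such a patient simply has no change score. That is a sensible intention, but it describes a variable and does not say how to handle a form completed late. Protocol 9.4.1.1 collects questionnaires at inclusion, which may fall on treatment, and the EQ-5D-5L missing-data rule deals only with missing items. A rule could sit in SAP Part II or Figure 1, neither of which was available.

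A reader might infer three further things that the documents do not support:

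- **A gap in resource-utilisation data.** This requires reading baseline as a late inclusion visit. The Annex 1 baseline form is anchored to treatment start, and on that anchor there is no gap.
- **Inflated SVR12 because early stoppers are never approached.** Nothing in the documents shows that this happened.
- **WPAI escapes the problem because only employment status and absenteeism remain.** Absenteeism is still tabulated at baseline, so it does not.

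**Conclusion.** The concern holds as a conflict between sections and a missing rule. It does not show that results are biased. SAEs between first dose and consent may or may not be captured, depending on which section a site followed. Up to 24.6% (12 weeks) or 14.1% (24 weeks) of an individual's treatment-emergent window is affected. If nobody consented after day 1 the effect is nil, and that number is not given. Under the stated assumptions the loss runs from almost nothing to about 1.4 patients in 55. The upper end requires all 55 to consent at day 28 and a 10% SAE risk. The effect is therefore probably small beside sampling error, but it can only lower the SAE percentage.

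For the EQ-5D-5L, the size and direction are unknown; the 0.002 to 0.05 range rests wholly on assumed inputs. The visible disposition text (SAP 4.2.5) does not ask for the number consented after day 1, so a reader of the report could not judge either effect. The point merits a change because the remedy is cheap, with medium confidence given the material not seen.

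**What to change.** 1. **SAE period.** Reconcile Protocol 11.1.4 with Protocol 9.7.6, 11.1.5 and Annex 1 and with SAP 4.2.8.3, so that the collection period and the serious treatment-emergent window match for patients consented late. If looking back in the charts is no longer feasible, footnote the TEAE and SAE tables as possibly incomplete before consent. The protocol version is dated 26 March 2018 and data collection ends in April 2018, so the footnote is the realistic route.
2. **Questionnaire baseline.** In the SAP, define the EQ-5D-5L and WPAI baseline as a questionnaire completed on or before study day 1. Show later first questionnaires separately, outside the baseline summaries and change scores.
3. **Disclosure.** Add the number consented after day 1 to the disposition table. Provide one TEAE/SAE sensitivity table, overall column only, in patients consented on or before day 1.

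The enrolment window is deliberate and can stay. The work is a SAP sentence or two, one table row, a footnote and one extra table, ahead of a final report due in January 2019. It assumes that consent and questionnaire dates are recorded.

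The real cost is precision in the EQ-5D-5L change analysis. If 25% or 50% of its patients lacked a valid baseline (assumed shares), standard errors would grow by factors of 1/√0.75 = 1.15 or 1/√0.50 = 1.41. The resulting number of patients cannot be stated, because the analysis is in the core population, not in all 50-55 enrolled. In the sensitivity table, numbers will be small and intervals wide; its use is to show whether the result changes grossly.
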